Measures of outcome: The outcome is type of treatment for BPD (surgical, pharmacological and other types of treatment)

Statistics: We will use Fisher's exact test and t-test to compare patients' baseline characteristics with 95% confidence intervals (CI) and p-values. For each treatment type we will use logistic regression model to investigate differences in outcome distribution between patients with and without psychiatric comorbidity. The logistic regressions will be performed with 95% CI adjusted for the following confounders: age, sex, CCI, level of education, equivalent available income, type of BPD (IBD, DBD or UBP) and marital status.

Study 3) Effect of psychiatric comorbidity in pharmacological treatment of BPD.

Aim: 1) To compare dosages of pharmacological treatment in BPD patients with and without the presence of psychiatric comorbidity in a nationwide Danish cohort study in 2010-2014. 2) To compare high vs. low dosages of pharmacological treatment for BPD in patients with BPD and psychiatric comorbidity.

Hypothesis: 1) Patients with BPD and psychiatric comorbidity are prescribed a higher dosage of pain medication for BPD compared with BPD patients without psychiatric comorbidity. 2) BPD patients with a psychiatric comorbidity with a high (defined as above the 50th percentile) vs. low (defined as below the 50th percentile) dosage of pain medication are also prescribed higher dosages of psychiatric medication.

Design and study population: The study will be a nationwide register-based cohort study. The study population consists of patients with BPD that received pharmacological treatment for BPD. In the secondary analysis the study population consists of patients with BPD and a psychiatric comorbidity, who received pharmacological treatment for BPD.

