Procedure: BPD patients will be identified via the DNPR. Pharmacological treatment of BPD will be defined as any treatment with the following drugs: NSAID (ATC: N01A*), Acitomenophen (ATC: N02BE01), Opioids (N02A*)¹³. Pharmacological treatment for psychiatric comorbidity will be defined as any treatment with the following drugs: Antipsychotics (ATC:N05A), Antidepressants (ATC: N06A), Selective Serotonin Reuptake Inhibitors (SSRI) (ATC: N06AB), and anxiolytics (ATC: N5B*)⁴¹. Pharmacological treatment that can be used in the treatment of both BPD and psychiatric disorders will be defined as any treatment with the following drugs: Antiepileptics (ATC: N03A) and Tricyclic antidepressants (ATC: N06AA). All data on pharmacological treatment will be identified using the Register of Medicinal Products Statistics⁷. From time of BPD diagnosis and the following three years, pharmacological treatment for both somatic illness and psychiatric comorbidity in Daily Defined Dosage (DDD) per year will be calculated⁴².

Information on somatic comorbidity for calculation of Charlson Comorbidity index³⁹ (CCI) at time of BPD diagnosis, will be retrieved from the DNPR. Data on psychiatric comorbidity will be identified using NPD-Psych. Information on marital status, vital status, and immigration status will be retrieved from the Civil Registration System (CPR)³⁵. Patients that are not alive or have emigrated within three years after BPD diagnosis are considered lost to follow-up and excluded from the cohort. Descriptive data on the socioeconomic status, education level and equivalent available income will be retrieved from Statistics Denmark³⁸. All data comprising each variable will be retrieved from 1th of January 2007 to 31th of December 2017 (three years before and after study period).

Measures of outcome: Primary outcome is pharmacological treatment in DDDs defined as high (above the 50th percentile and low (below the 50th percentile) of pain medication. Secondary outcome is psychiatric medication in BPD patients with psychiatric comorbidity in DDD's defined according to high (above the 50th percentile) and low (below the 50th percentile) dosages of pain medication.

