Statistics: We will use Fisher's exact test and t-test to compare patients' baseline characteristics with 95% confidence intervals (CI) and p-values. Time dependent Cox regression will be performed separately for patients with specific and unspecific BPD to examine dosage of pharmacological treatment over time comparing patients with and without psychiatric comorbidity. The analysis will be performed with 95% CI and adjusted for the following confounders: age, sex, CCI, level of education, equivalent available income, marital status and the presence of psychopharmacological treatment.

To examine dosage of psychopharmacological treatment over time comparing patients with psychiatric comorbidity and low vs high dose of pharmacological treatment of BPD, time dependent Cox regression will be performed reporting 95% CI and adjusting for the following confounders: age, sex, CCI, level of education, equivalent available income, marital status.

Psychiatric comorbidity in Back Pain Disorders
Risk, treatment and pharmaco-epidemiological analysis

Ethics

All studies will be based on national clinical registries and approval is obtained by The Danish Health Data Board and the Danish Data Protection Agency (18/3337). According to Danish law, further ethical approval is not required for purely registry-based studies. All data will be stored on Statistics Denmark's servers and will be anonymized ensuring no patients can be identified.

PhD Outline

The PhD will be conducted within a timeframe of three years (six semesters).

	1st semester	2nd semester	3rd semester	4th semester	5th semester	6th semester
Data collection	X					
PhD Courses	X	X	X			
Data analysis		X	X	X	X	
Writing articles			X	X	X	X

References

1. Hawker GA. The assessment of musculoskeletal pain. *Clinical and experimental rheumatology* 2017;35 Suppl 107(5):8-12.

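### Study 3 has no overall estimate for hypothesis 1, and BPD type is only partly controlled in its first analysis and not at all in its second

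*Combined protocol and SAP*

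**What the plan says.** The aim, hypothesis and population of Study 3 are stated for BPD patients as a whole. Aim 1 is "To compare dosages of pharmacological treatment in BPD patients with and without the presence of psychiatric comorbidity". Hypothesis 1 reads "Patients with BPD and psychiatric comorbidity are prescribed a higher dosage of pain medication for BPD compared with BPD patients without psychiatric comorbidity". On the population: "The study population consists of patients with BPD that received pharmacological treatment for BPD". None of these mentions BPD type.

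The Statistics paragraph of Study 3 then gives one analysis for this comparison: "Time dependent Cox regression will be performed separately for patients with specific and unspecific BPD". Its covariates are demographic and socioeconomic variables, the Charlson index and use of psychopharmacological treatment. BPD type is not among them.

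A second Cox model in the same section compares psychiatric medication between patients with high and low pain-medication dose. It is not described as split by BPD type, and its covariate list also omits type.

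Elsewhere the plan works with three types. The Introduction divides specific BPD into IBD and DBD, on grounds of cause and treatment options, beside an unspecific group. The Statistics paragraph of Study 1 analyses the three groups. The Study 2 confounder list ends with "type of BPD (IBD, DBD or UBP) and marital status".

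**The concern.** Two gaps follow.

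- **No answer at the level of the hypothesis.** Hypothesis 1 makes one statement about all treated BPD patients. The analysis will return two hazard ratios. If one stratum shows an association and the other does not, the plan does not say whether the hypothesis is supported, and without an interaction test it cannot say whether the two results differ by more than chance.
- **Uneven control of BPD type.** In Study 2 the plan treats type as a confounder when the exposure is psychiatric comorbidity and the outcome is treatment. In Study 3, with the same exposure and treatment dose as outcome, only the specific/unspecific part of type is handled. In the second model none of it is. A difference in disease mix between the groups compared could then be read as an association with comorbidity, or with pain-medication dose.

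**Working it through.** The documents give no sample size, event count, significance level or type distribution for Study 3, so there is no planned figure to reproduce. The main check is a comparison of the texts. The calculations after it are illustrations on assumed inputs.

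**1. Handling of BPD type across the plan**

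| Analysis | Population of the claim | Handling of BPD type |
|---|---|---|
| Study 1, Statistics | BPD versus background population | IBD, DBD and UBP analysed as groups |
| Study 2, Statistics | All BPD | IBD/DBD/UBP as covariate |
| Study 3, first model | All treated BPD | Separate models, specific and unspecific; IBD/DBD not separated |
| Study 3, second model | Treated BPD with psychiatric comorbidity | None stated |

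Study 2 has an aim and a hypothesis on BPD subgroups. Study 3 has neither, so the split in its first model is not tied to a stated question.

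**2. Effect of having no rule for two results**

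Assume a 5% test in each stratum; the plan mentions only 95% confidence intervals. The strata contain different patients, so the tests are independent.

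- No true association, hypothesis counted as supported if either stratum is significant: 1 − 0.95² = 0.0975.
- No true association, both required: 0.05² = 0.0025.
- True association, assumed 80% power in each stratum: either 1 − 0.2² = 0.96; both 0.8² = 0.64.

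The chance of declaring hypothesis 1 supported thus depends heavily on a rule that is not written down.

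**3. Possible confounding by IBD/DBD in the specific-BPD model**

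Let p1 and p0 be the IBD share with and without psychiatric comorbidity, and RR the IBD/DBD ratio for the outcome. The omitted variable multiplies the estimated ratio by

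(p1(RR − 1) + 1) / (p0(RR − 1) + 1).

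Assume p0 = 0.10 throughout:

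| p1 | RR = 0.5 | RR = 2.0 |
|---|---|---|
| 0.10 | 1.000 | 1.000 |
| 0.15 | 0.925/0.950 = 0.974 | 1.15/1.10 = 1.045 |
| 0.20 | 0.900/0.950 = 0.947 | 1.20/1.10 = 1.091 |
| 0.30 | 0.850/0.950 = 0.895 | 1.30/1.10 = 1.182 |

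The range is about 0.90 to 1.18, in either direction, with no bias if the mix is equal. The formula is only a rough guide to a hazard ratio, and it ignores whatever the planned covariates already absorb. This bias would not shrink with sample size.

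**4. Precision**

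By Schoenfeld's formula, power = Φ(√(D·q(1 − q))·|ln HR| − 1.96), where D is the number of events and q the comorbid share. Assume D = 1000, q = 0.30 and HR = 1.2.

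- Pooled: √210 × 0.182 = 2.64, power 75%.
- Events split 50:50: 46% in each stratum.
- Events split 20:80: 22% and 66%.

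A nationwide register may have far more events, and this loss may then be negligible. The case for an overall model therefore rests on interpretation, not on power.

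**The case against.** The strongest reply is that separate models are a sound choice. The Introduction criticises earlier work for pooling heterogeneous back pain groups, Study 1 expects unspecific and specific patients to differ in psychiatric risk, and Study 2 uses the same split. Separate models control the specific/unspecific difference at least as fully as a covariate would, and they let every covariate effect vary by stratum. A pooled figure could hide heterogeneity that the authors want to see. All of this stands. It is a reason to keep the separate models, but it does not supply the missing overall estimate or interaction test.

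Three stronger readings are tempting, and the documents do not support them.

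- A reader might infer that all of Study 3 is split by type. Only the hypothesis 1 analysis is; the second model is not described as split.
- A reader might infer that hypothesis 1 goes unexamined, or that BPD type is ignored in its analysis. The two strata together cover the study population, and the only part of type left uncontrolled there is IBD versus DBD, in the specific-BPD model.
- A reader might infer a bias of a definite size, for example a percentage of mean dose. The documents give neither the IBD share by comorbidity nor the dose by type. The outcome is also not mean dose: "Primary outcome is pharmacological treatment in DDDs defined as high (above the 50th percentile and low (below the 50th percentile) of pain medication", analysed by Cox regression.

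The Study 2 precedent is also less direct for the second model, where the exposure is pain-medication dose and the outcome psychiatric medication. Type still needs to be considered there, because the plan forms its groups partly on treatment options, which makes a link with pain medication plausible.

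**Conclusion.** The point holds as a minor one. Three facts rest on the text alone: hypothesis 1 has no overall estimate or interaction test; IBD and DBD are pooled without adjustment in the specific-BPD model; and the second model neither splits by nor adjusts for BPD type. Nothing elsewhere in the document fills these gaps.

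Whether they bias the results is conditional. Confounding arises only if type is associated with both exposure and outcome after the planned adjustment, and neither its size nor its direction can be determined from the documents. The multipliers shown above are illustrations of scale and not estimates for this cohort.

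**What to change.** Change the Statistics paragraph of Study 3 as follows.

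1. Add one overall model in all treated BPD patients, stratified by or adjusted for BPD type (IBD, DBD, UBP), and name it as the test of hypothesis 1.
2. Add a comorbidity-by-type interaction test, and keep the separate specific and unspecific models as type-specific analyses.
3. Add an IBD/DBD term to the specific-BPD model.
4. Add BPD type (IBD, DBD, UBP) to the covariates of the second model.

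For the overall and type-specific results to be comparable, the text should also define the event in the Cox model and say whether the 50th percentile is taken over all treated BPD patients or within each type. The plan currently states neither.

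The cost is a few lines of wording and a little extra analysis. Study 2 already requires the type variable, so no new data are needed.

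### Study 3's model for Aim 1 adjusts for psychotropic drug use, which is largely downstream of psychiatric comorbidity, so it may not estimate the overall difference the aim asks about

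*Combined protocol and SAP*

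**What the plan says.** Hypothesis 1 of Study 3 is that "Patients with BPD and psychiatric comorbidity are prescribed a higher dosage of pain medication for BPD" than BPD patients without such comorbidity. The outcome behind it is given as "Primary outcome is pharmacological treatment in DDDs defined as high (above the 50th percentile and low (below the 50th percentile", for pain medication. Under Statistics, "Time dependent Cox regression will be performed separately for patients with specific and unspecific BPD", to examine dosage over time "comparing patients with and without psychiatric comorbidity". The adjustment set is age, sex, Charlson index, education, income, "marital status and the presence of psychopharmacological treatment", all described as confounders.

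The Procedure of Study 3 says what psychiatric drug treatment is: "Pharmacological treatment for psychiatric comorbidity will be defined as any treatment with the following drugs", followed by antipsychotics (N05A), antidepressants (N06A), SSRIs (N06AB) and anxiolytics. A separate class, usable for both BPD and psychiatric disorders, holds antiepileptics (N03A) and tricyclics (N06AA). On timing it says: "From time of BPD diagnosis and the following three years, pharmacological treatment for both somatic illness and psychiatric comorbidity" will be calculated in DDD per year.

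Two neighbouring analyses treat the variable differently. The Study 2 models use the same exposure and do not adjust for psychotropic use. The second Study 3 model has psychotropic dosage as its outcome.

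**The concern.** A confounder should precede the exposure or share a cause with it. Here the covariate is, by the plan's own definition, treatment of the exposure, and the only measurement window given for these drugs is the one in which the outcome accrues. Adjusting for it holds fixed something that psychiatric comorbidity itself largely brings about.

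The question is about an overall difference. The thesis aim asks whether psychiatric comorbidity affects dosages, and Aim 1 and Hypothesis 1 compare patients with and without it. Nowhere does the plan ask for the part of the difference that does not run through psychiatric drug treatment. As this is the only model planned for Hypothesis 1, a weak or null result could not be read: it might mean no difference, or a difference absorbed by the covariate.

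**Working it through.** **Role of the variable in the plan**

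- Exposure: a hospital psychiatric diagnosis from three years before to three years after BPD diagnosis (Setting and study population).
- Covariate: any use of drugs defined as treatment of that exposure. The drug calculations run from BPD diagnosis for three years (Study 3, Procedure). The Statistics paragraph gives the covariate no window of its own.
- Outcome: pain-drug dosage over the same three years.
- Overlap: N06AA lies within N06A, so the psychiatric list contains tricyclics, which the plan calls usable for both conditions and counts as BPD treatment in Study 2. Whether the dual-use antiepileptics enter the covariate is not stated.

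**Size**

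The plan gives no sample size, effect size or drug-use figures for Study 3, so there is no stated figure to reproduce. Every input below is an assumption. Let p1 and p0 be the shares using psychotropics with and without comorbidity, bX the direct effect of comorbidity on the probability of high pain dosage, and bM the effect of psychotropic use. With no interaction and no other confounding:

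- total effect = bX + bM × (p1 − p0)
- share removed by adjustment = bM × (p1 − p0) / total effect

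| bX | bM | 60% vs 35% | 70% vs 25% | 80% vs 15% | 90% vs 10% |
|---|---|---|---|---|---|
| 0.10 | 0.05 | 11% | 18% | 25% | 29% |
| 0.10 | 0.10 | 20% | 31% | 39% | 44% |
| 0.05 | 0.05 | 20% | 31% | 39% | 44% |
| 0.05 | 0.10 | 33% | 47% | 57% | 62% |
| 0.10 | 0 | 0% | 0% | 0% | 0% |
| 0.10 | −0.05 | −14% | −29% | −48% | −67% |

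The largest entry is 0.10 × 0.80 = 0.08 removed from a total of 0.05 + 0.08 = 0.13, or 62%. In the last row the adjusted effect exceeds the total: for 90% vs 10%, the total is 0.10 − 0.05 × 0.80 = 0.06 against 0.10 adjusted.

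The plan uses Cox regression, so the same structure was simulated as time to high dosage (60,000 patients, 10% exposed, baseline hazard 0.2 per year, three years, direct HR 1.3):

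| Use, exposed vs unexposed | Psychotropic HR | HR without covariate | HR with covariate | Share of log-HR removed |
|---|---|---|---|---|
| 60% vs 35% | 1.3 | 1.378 | 1.295 | 19% |
| 70% vs 25% | 1.3 | 1.481 | 1.316 | 30% |
| 80% vs 15% | 1.3 | 1.525 | 1.292 | 39% |
| 80% vs 15% | 1.6 | 1.733 | 1.284 | 55% |
| 80% vs 15% | 1.0 | 1.296 | 1.316 | −6% (simulation noise) |

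**How closely the covariate tracks the exposure**

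With pX the share exposed and pM = pX·p1 + (1 − pX)·p0, the correlation is phi = (p1 − p0) × √[pX(1 − pX) / (pM(1 − pM))]. For pX = 0.10 and use of 70% vs 25%, pM = 0.295 and phi = 0.45 × √(0.09 / 0.208) = 0.30. Over 5–20% exposed and the four use pairs, phi runs from 0.11 to 0.73 and the variance inflation 1/(1 − phi²) from 1.01 to 2.14.

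**The case against.** The best defence is that psychotropic use stands in for psychiatric illness the exposure misses. The Introduction concedes that primary care is not fully covered and that only severe diagnoses are captured. Because a qualifying diagnosis may also follow the BPD diagnosis by up to three years, some drug use can precede the recorded exposure. Both points stand, and they are why the covariate is called largely, not wholly, downstream. They do not justify the model as written: the plan gives no such rationale, and use during follow-up also captures treatment of the registered exposure.

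A second defence is that the three-year window is stated for DDD per year, whereas the model uses mere presence of treatment, and data are retrieved from 2007. That is fair, but it leaves the timing undefined; it does not supply a pre-exposure window.

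A reader might also infer more than the documents support:

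- That the covariate is a near-proxy for the exposure. No concordance figure is given, users without a hospital diagnosis are to be expected, and phi is only moderate in most of the scenarios above.
- That the bias must be toward no difference. This requires psychotropic use to go with higher pain dosage, which is not established.
- That Hypothesis 2, under which high-dose patients "are also prescribed higher dosages of psychiatric medication", shows the drugs to be a consequence of the exposure. It concerns only patients who all have comorbidity, so the exposure does not vary there.
- That antiepileptics are part of the covariate. They are listed only in the dual-use class.

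**Conclusion.** The point holds. The model for Aim 1 adjusts for treatment of its own exposure, with no window before the exposure, no stated direct-effect question and no companion model without the covariate. If psychotropic use is related to pain dosage, the model does not estimate the difference that Aim 1 and Hypothesis 1 describe.

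The structural conclusion rests on the plan's own definitions; the size and sign do not. With a zero or positive association, the assumed inputs give 0% to roughly 60% of the effect removed. With a negative association, adjustment inflates the effect. No single figure within that range can be defended from the documents.

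**What to change.** In the Statistics paragraph of Study 3, remove psychotropic treatment from the adjustment set of the main model for Aim 1, leaving age, sex, Charlson index, education, income and marital status. Report the model that includes it as a labelled secondary analysis (direct-effect or sensitivity). State the window in which use counts, whether tricyclics are included through N06A, and whether the dual-use antiepileptics are included.

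If the covariate is meant to capture psychiatric illness treated only in primary care, say so and restrict it to use before both the psychiatric and the BPD diagnosis; for patients without a psychiatric diagnosis, only the BPD date applies. Data start on 1 January 2007 and the exposure window reaches back three years. The look-back before the earliest qualifying psychiatric diagnosis therefore runs from none (BPD diagnosed at the start of 2010) to about five years (end of 2014), and the plan should say how that is handled.

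The change needs no new data. It costs one extra model to report, fitted in each of the two BPD groups, and gives up some control in the main model for psychiatric illness not captured in the hospital register.

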When investigating psychiatric comorbidity in BPD patients, focusing on anxiety and depression, has been the norm. However, important information on the relationship between other types of mental illness and back pain disorders might be identified, if a dataset of sufficient size and quality, is used for analysis. A population-based set of registry data as the ones available in Denmark provides this. By grouping psychiatry comorbidity according to ICD-10, mental illnesses with common pathways are analyzed together. In the ICD-10 system psychiatric diagnosis are grouped according to symptomatology and common etiology³⁰. All psychiatric diagnoses are considered relevant in the chosen population, as any psychiatric disorders represents a vulnerable patient with possible complicating factors when treating back pain. The limitation of Danish registry-based data is, that it does not provide complete data from the primary care sector selecting only severe psychiatric diagnosis. In conclusion, back pain disorders and the association with psychiatric comorbidity has primarily been investigated using symptomatology, not ICD-10 diagnoses and with a focus on anxiety and depression. The studies are small, heterogeneous and of varying quality. The use of pharmacological treatment, including opioids, in back pain disorders complicated by psychiatric comorbidity is unknown.

Aim of the thesis

The aim of this PhD thesis is to use population-based registry data to:

1) to estimate the prevalence of psychiatric comorbidity in patients with back pain disorders (BPD) compared to patients with no back pain in the time period 2010-2014; 2) Investigate whether presence of psychiatric comorbidity affects utilization of pharmacological, surgical and other types of treatment for patients with BPD 3) Investigate whether presence of psychiatric comorbidity affects utilization and dosages of pharmacological treatment for patients with BPD.

Clinical contributions of this PhD

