Psychiatric comorbidity will be defined as the presence of any of the following diagnosis, according to ICD-10 classification³⁰, obtained from the National Patient Registry – Psychiatry (NPD-Psych), covering all inpatient and outpatient psychiatric services in Denmark in the time period 1th January 2007 to 31th December 2017: Organic, including symptomatic, mental disorders (F00-DF09), Mental and behavioral disorders due to psychoactive substance use (F10-F19), Schizophrenia, schizotypal and delusional disorders (F20-F29), Mood [affective] disorders (F30-F39), Neurotic, stress-related and somatoform disorders (F40-F48), Behavioral syndromes associated with physiological disturbances and physical factors (F50-F59), Disorders of adult personality and behavior (F60-F69), Mental retardation (F70-F79), Disorders of psychological development (F80-F89), Behavioral and emotional disorders with onset usually occurring in childhood and adolescence (F90-F98) and, Unspecified mental disorder (F99). To qualify as a psychiatric comorbidity to back pain disorder, we define that the psychiatric diagnosis must be given no earlier than three years prior to back pain disorder diagnosis and no later than three years after.

Study 1) Prevalence of psychiatric comorbidity in back pain disorders

Psychiatric comorbidity in Back Pain Disorders
Risk, treatment and pharmaco-epidemiological analysis

Aim: 1) To estimate prevalence of psychiatric comorbidity in patients with BPD compared to patients without BPD and 2) To estimate prevalence of psychiatric comorbidity in patients with unspecific back pain (UBP) compared to the background population and to patients with a specific back pain (SBP) in a Danish nationwide cohort from 2010-2014.

Hypothesis: 1) There is a higher risk of psychiatric comorbidity in BPD patients compared to the background population and 2) UBP patients have a higher risk of psychiatric comorbidity compared to patients with specific BPD.

Design: The study will be a nationwide register-based matched cohort study.

Procedure: Selected BPD patients with the following diagnosis will be identified via the DNPR: Spondylopathies DM45-49, Other dorsopathies DM 50-54 and Segmental and somatic dysfunction DM99. Each patient will be matched 1:5 on age and sex with patients without back disorders by random at Statistics Denmark³⁸. The selection of diagnosis is to be able to match the population with non-BPD patients in the Danish registries.

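### Study 3's second model pools all psychiatric diagnoses without adjusting for which diagnosis a patient has, so diagnosis mix may confound the high versus low pain-dose contrast

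*Combined protocol and SAP*

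**What the plan says.** The second hypothesis of Study 3 is that patients with psychiatric comorbidity and a high "dosage of pain medication are also prescribed higher dosages of psychiatric medication". High and low are defined by a median split. Under Measures of outcome: "Secondary outcome is psychiatric medication in BPD patients with psychiatric comorbidity in DDD's defined according to high" and low pain-drug dose.

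The population is pooled. Under Design and study population: "In the secondary analysis the study population consists of patients with BPD and a psychiatric comorbidity" who were treated pharmacologically for back pain disorder (BPD). Under Setting and study population: "Psychiatric comorbidity will be defined as the presence of any of the following diagnosis", followed by eleven ICD-10 blocks from F00 to F99. A diagnosis qualifies if it falls within three years before or three years after the BPD diagnosis.

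The psychiatric drugs in Study 3, Procedure, are "Antipsychotics (ATC:N05A), Antidepressants (ATC: N06A), Selective Serotonin Reuptake Inhibitors (SSRI) (ATC: N06AB), and anxiolytics (ATC: N5B" and related codes. Amounts are counted over the three years from the BPD diagnosis.

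The model is described under Study 3, Statistics: "comparing patients with psychiatric comorbidity and low vs high dose of pharmacological treatment of BPD, time dependent Cox regression will be performed", "adjusting for the following confounders: age, sex, CCI, level of education, equivalent available income, marital status".

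The nearest mitigating text is in the Introduction: "By grouping psychiatry comorbidity according to ICD-10, mental illnesses with common pathways are analyzed together". No Study 3 analysis carries this through as a covariate, a stratification or a sensitivity analysis.

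**The concern.** A confounder has to be related to both the exposure and the outcome. Psychiatric diagnosis plausibly is.

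- **Outcome.** Antipsychotics, antidepressants and anxiolytics are prescribed for different disorders. The expected amount can therefore differ between, say, the schizophrenia block, the neurotic and stress-related block and the developmental block.
- **Exposure.** The Introduction cites substance abuse disorder in up to 43% of BPD patients on opioids. It treats the link between other specific disorders and opioid consumption as an open question, so the plan itself regards pain-drug use as something that may vary by disorder.

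If the mix of disorders differs between the high and low pain-dose groups, their psychiatric-drug use can differ even when pain dose and psychiatric dose are unrelated among patients with the same disorder. The reverse can also happen: an association within disorders can be diluted. This is the only model that tests hypothesis 2. A large national cohort would narrow the interval around a confounded estimate without moving it.

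**Working it through.** The plan gives no sample size, effect size, DDD by diagnosis or diagnosis mix by pain dose for Study 3, so there is no figure to reproduce. What follows is illustration on assumed inputs.

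**1. Is diagnosis represented in the model?** The listed covariates are age, sex, CCI, education, income and marital status. Study 3, Procedure, describes CCI as somatic comorbidity. No other section adds a psychiatric term to this model.

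**2. Mean DDDs, with no association inside any diagnosis group.** Assume two groups: a share p of patients with mean m1 = 450 DDD/year, and the rest with m0 = 150. Let a be the proportion of the first group above the pain-dose median. Half of all patients are above the median, so the first group's share is h = 2pa in the high-dose half and l = 2p(1 − a) in the low-dose half.

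Ratio = [h·m1 + (1 − h)·m0] / [l·m1 + (1 − l)·m0]

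| p | a | h | l | Mean, high | Mean, low | Ratio |
|---|---|---|---|---|---|---|
| 0.15 | 0.40 | 0.12 | 0.18 | 186 | 204 | 0.91 |
| 0.15 | 0.60 | 0.18 | 0.12 | 204 | 186 | 1.10 |
| 0.25 | 0.35 | 0.175 | 0.325 | 202.5 | 247.5 | 0.82 |
| 0.25 | 0.65 | 0.325 | 0.175 | 247.5 | 202.5 | 1.22 |

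First row: 0.12 × 450 + 0.88 × 150 = 186, and 0.18 × 450 + 0.82 × 150 = 204. The imbalances are 6 and 15 percentage points. With a = 0.50, h = l and the ratio is 1.

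**3. With a true within-group ratio.** If the same ratio holds in both groups, it multiplies the figures above. A true 1.10 would appear as 1.10 × 0.91 = 1.00, or as 1.10 × 0.82 = 0.90. Changing the sign needs a larger imbalance or DDD gap, relative to the true effect, than producing a spurious difference does.

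**4. Hazard-ratio scale.** The planned model is a Cox regression, but the plan does not define its event. Assume an event of reaching some psychiatric-drug dose, with baseline hazard 0.15 per year, 3 years of follow-up, and 40,000 simulated patients split equally between high and low pain dose. Shares are those of the higher-hazard diagnosis group.

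| True HR | Diagnosis HR | Share in high / low | HR without diagnosis (95% CI) | HR with diagnosis |
|---|---|---|---|---|
| 1.00 | 3 | 50% / 30% | 1.25 (1.22–1.29) | 1.00 |
| 1.00 | 2 | 40% / 30% | 1.08 (1.05–1.12) | 1.01 |
| 1.00 | 3 | 30% / 50% | 0.80 (0.78–0.82) | 0.99 |
| 1.25 | 3 | 30% / 50% | 1.00 (0.97–1.02) | 1.26 |
| 1.20 | 3 | 20% / 50% | 0.85 (0.83–0.88) | 1.22 |
| 1.20 | 3 | 40% / 40% | 1.17 (1.14–1.20) | 1.21 |

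The last row shows that a balanced mix causes no material bias. The small gap between 1.17 and 1.21 is the usual shift of a hazard ratio towards 1 when a strong predictor is left out.

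**5. When is diagnosis known?** Qualifying diagnoses may be made up to three years after BPD, which is the same window in which both drug amounts are counted. A term built from all qualifying diagnoses would therefore use information that did not exist at the start of follow-up.

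**The case against.** **The hypothesis may be descriptive.** It says that patients on high pain doses also receive more psychiatric medication. Read as a statement about co-prescribing, it makes diagnosis mix part of the answer. But the plan calls its covariates confounders, so it intends an adjusted comparison. Reporting the contrast with and without diagnosis terms serves both readings.

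**Adjustment can do harm.** This objection stands and shapes the fix. Fixed indicators that include diagnoses made after BPD would condition on the future. An F10-F19 diagnosis first made after BPD may be a consequence of pain-drug exposure, and adjusting for it could remove part of the association under study.

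**A fixed before/after label looks attractive.** Study 2 defines one, and a reader might infer that it measures how much of the three years was spent in psychiatric treatment. The documents do not support that. Diagnoses come from hospital psychiatric services, and the Introduction says that primary-care data are incomplete. A hospital diagnosis date therefore does not fix when drug treatment began, and an earlier diagnosis does not show that treatment continued.

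**All magnitudes are assumed.** This also stands. In addition, the mean-DDD ratios are not on the scale that a Cox model reports.

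**Conclusion.** The omission is certain from the text; the bias is possible, not demonstrated. Diagnosis mix may confound the high/low contrast in Study 3's second model, by an amount and in a direction that the documents do not give. Spurious mean-DDD ratios of about 0.8 to 1.2 rest on an assumed threefold gap in DDDs between two diagnosis groups, a 15% or 25% share for the larger-dose group, and 6 or 15 points of imbalance. With a balanced mix, bias is small.

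A reader might infer that diagnosis is the main driver of psychiatric DDDs, or that case mix will reverse the result. Neither has a source in the documents. Reversal appears only under some of the assumed inputs.

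The change should be made because the data are already retrieved and this model is the only test of hypothesis 2. The analysis is secondary, and the undefined Cox event is a separate matter that this change does not resolve.

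**What to change.** In Study 3, Statistics, second model:

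1. Add one indicator for each ICD-10 block in the comorbidity definition. Make them non-exclusive, so that a patient with several diagnoses has several indicators.
2. Set each indicator at the BPD date from qualifying diagnoses recorded on or before that date. For a diagnosis first made afterwards, switch the indicator on from its diagnosis date as a time-updated covariate. Do not use a fixed before/after label.
3. Report the high/low contrast with and without these terms. Note that a small change between the two need not mean confounding, as the balanced case above shows.
4. Add a sensitivity analysis that omits F10-F19 diagnoses first made after BPD, by holding that indicator at its value on the BPD date.

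Cost: modest extra coding. The diagnoses are already drawn from the psychiatric patient registry for Study 3, but the plan uses them only as a single any-diagnosis flag, and the dated, block-level indicators still have to be built. The model gains at most eleven parameters if each block has one coefficient.
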